4.3 Justification for Dose

The doses of AZD9977 for combination therapy were selected to enable characterisation of the dose-response for UACR and to evaluate safety in this patient population.

The wide (10-fold) range of doses for AZD9977 (15 to 150 mg) given in combination with dapagliflozin 10 mg and dapagliflozin treatment alone will provide a sufficiently large range of AZD9977 exposures to evaluate the dose/exposure response relationship between UACR and AZD9977 + dapagliflozin in relation to dapagliflozin alone. About one third of the dose is excreted as unchanged AZD9977 in urine suggesting that renal clearance is contributing to the overall elimination of AZD9977. The main metabolic enzyme for AZD9977 is CYP3A4 that may have changed capacity in patients with low renal function. **CC**

. The ongoing PK renal impairment study (D6401C00008) will confirm the PK profile of AZD9977 in patients with low renal function including those with an eGFR < 30 mL/min/1.73 m². This data will be available ahead of including patients with eGFR < 30 mL/min/1.73 m² into this study (D6402C00001). The dose selection for AZD9977 is based on PK, pharmacodynamic and safety data from previous studies in healthy subjects and in patients with HF. Using in vitro and clinical literature data for eplerenone, a translational PK/pharmacodynamic model for UACR reduction was developed. This model could well predict the UACR reduction for both spironolactone and finerenone assuming the same in vitro: in vivo ratio for IC50 and was therefore used to predict the UACR reduction for AZD9977. The 3 selected doses of AZD9977 are anticipated to yield an effect on UACR covering the whole dose-response curve from approximately 20 to 60% UACR reduction.

Dapagliflozin is currently under investigation in HF patients with LVEF >40% (HFmrEF and HFpEF) in the DELIVERostudy (NCT03619213). The dapagliflozin dose of 10 mg once daily is approved for treatment of patients with T2DM, for patients with heart failure and reduced ejection fraction with or without T2DM, and for patients with chronic kidney disease with or without T2DM.

There is a low risk for metabolic drug-drug interactions between AZD9977 and dapagliflozin. AZD9977 is mainly eliminated by CYP3A4-mediated metabolism and dapagliflozin is not an inhibitor of that metabolic enzyme (Kasichayanula et al 2012). Dapagliflozin is mainly eliminated by UGT1A9-mediated metabolism and AZD9977 is not an inhibitor of that metabolic enzyme.

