9.2 Sample Size Determination

A total of 119 evaluable participants per arm will provide 80% power to detect a 30% difference in a AZD9977 dose group combined with dapagliflozin 10 mg compared to dapagliflozin 10 mg alone in percent change from baseline in UACR at 12 weeks, assuming a SD of 1.0 on the natural log-scale and alpha = 0.05. To account for approximately 5% drop-out from the study, approximately 500 participants will be randomly assigned to study intervention (125 participants per group) such that approximately 476 evaluable participants (119 per group) complete the study.

Patients randomised according to CSP versions 1.0 to 5.0 (before dropping placebo and AZD9977 150 mg monotherapy arms) will be considered as part of Cohort 1, while patients randomised subsequently will be included in Cohort 2. The primary analysis for the remaining 4 treatment groups will combine data from both cohorts, while the accrued data from discontinued treatment groups will be analysed descriptively.

9.3 **Populations for Analyses**

The following populations are defined:

Population/Analysis set	Description	
Enrolled	All participants who sign the main ICF.	
Full Analysis Set (FAS)	All participants who are randomised and either receive or do not receive any study intervention. Participants are evaluated according to the treatment assigned at randomisation. The FAS will be used for all analyses of demographic baseline characteristics and efficacy data.	
Per Protocol Set (PPS)	A subset of the FAS consisting of all participants who do not violate the terms of the protocol in a way that may affect the primary efficacy endpoint significantly. All decisions to exclude participants from the per protocol analysis set will be made and documented prior to the unblinding of the study.	
Safety Set (SS)	 All participants who are randomised and receive any study intervention. Participants are evaluated according to the actual treatment they received. If a participant received a different treatment dose than randomised throughout the study, they will be analysed according to the treated dose, not the randomisation dose. If a participant received study drug from the wrong kit for only part of the treatment duration, they will be analysed according to their randomisation dose. The SS will be used for all safety analyses. 	

Table 7Populations for Analysis

Additional analysis sets, such as PK population may be defined the SAP for exploratory analyses.

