9.4.2.1 Primary Endpoint

The primary efficacy endpoint for this study is the percent change from baseline in UACR at 12 weeks.

Baseline for UACR will be defined as the geometric mean of 3 UACR values derived from samples collected at consecutive days prior to the first dose of study treatment.

As UACR is assumed to follow a log-normal distribution, it will be log transformed for statistical analysis purposes. The mean log percent changes in UACR at 12 weeks for each of the 3 doses of AZD9977 combined with dapagliflozin 10 mg and dapagliflozin 10 mg alone will be estimated in a mixed model for repeated measures (Visits 7, 8, 9, and 10). The values will be back-transformed onto the original scale to give the geometric mean relative percent change from baseline at 12 weeks.

Patients randomised according to CSP versions 1.0 to 5.0 (before dropping placebo and AZD9977 150 mg monotherapy arms) will be considered as part of Cohort 1, while patients randomised subsequently will be included in Cohort 2. The primary analysis for the remaining 4 treatment groups will combine data from both cohorts, while the accrued data from discontinued treatment groups will be analysed descriptively.

The analysis model will include UACR baseline value, treatment, and visit as fixed effect, and the stratifying factors (T2DM [yes/no] and eGFR [≥ 20 to < 30 mL/min/1.73 m²; or ≥ 30 to < 45 mL/min/1.73 m²; or ≥ 45 mL/min/1.73 m²]) as well as the Cohort variable (1 or 2) as covariates. Moreover, treatment-by-visit interaction will also be included in the model. The final analytical approach will be described in detail in the SAP. For the primary analysis, the main treatment comparisons to be evaluated are (in a fixed-sequence testing):

- 1 Overall comparison of the percentage changes from baseline in UACR at week 12 across all 4 treatment groups
- 2 Each of the 3 doses of AZD9977 in combination with dapagliflozin 10 mg versus dapagliflozin 10 mg in the following order:
 - 1. AZD9977 150 mg + dapagliflozin 10 mg versus dapagliflozin 10 mg
 - 2. AZD9977 50 mg + dapagliflozin 10 mg versus dapagliflozin 10 mg
 - 3. AZD9977 15 mg + dapagliflozin 10 mg versus dapagliflozin 10 mg

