Section 1.1 Synopsis Section 9.2 Sample Size Determination	Update for sample size and drop-out rate, also for an interim analysis	The sample size and the drop-out rate have been updated according to the new study design. The expected effect size was reduced due to the fact that the new comparator is an active drug (dapagliflozin 10 mg).
Section 1.2 Schema	Update of the figure concerning the study design	The figure was updated according to the new study design.
Section 1.3 Schedule of Activities	Time windows for Visits 2 and 5 to 10 were amended: Visit 2: -10 to -3 days Visit 5: \pm 2 days Visits 6, 7, 8, 9 and 10: \pm 3 days Visit 11: \pm 4 days	To allow for flexibility in scheduling for sites and subjects and adjustment to fit with number of tablets in one dapagliflozin bottle for the safety follow-up.
Section 1.3 Schedule of Activities	Inclusion of central laboratory serum/plasma samples for K ⁺ , creatinine including eGFR calculation at Visit 2	To have values from central laboratory closer to randomisation Visit 3.
Section 1.3 Schedule of Activities	Removal of PK sampling on Day 64	Reduction of sampling procedures and blood volume to lessen burden on sites and subjects.
Section 1.3 Schedule of Activities	Reduction of number of PD sampling visits (NT-proBNP, aldosterone, renin, ACTH, cortisol, copeptin, and FPG) from 9 to 5 visits (visits 3, 5, 7, 10, 11)	Reduction of sampling procedures and blood volume to lessen burden on sites and subjects.
Section 1.3 Schedule of Activities	Inclusion of dapagliflozin 10 mg treatment after the EOT visit	To do safety follow-up under the same standard of care (dapagliflozin) as during run-in.

Section Number and Name	Description of Change	Brief Rationale
Section 1.3 Schedule of Activities Section 3 Objectives and Endpoints Section 4.2 Scientific Rationale for Study Design Section 8.1.2.1 Transthoracic Echocardiography-derived Parameters	Removal of transthoracic echocardiography; removal of the applicable exploratory objective	Lessen the operational study complexity in order to reduce burden on sites and subjects. Extensive central echo protocol and needed to transfer data for central reading. In addition, local echocardiography is already being conducted at screening to confirm HF diagnosis.

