#### 4.10.1.1 Analysis of the primary efficacy endpoint

Patients randomised according to CSP versions 1.0 to 5.0 (before dropping placebo and AZD9977 150 mg monotherapy arms) will be considered as part of Cohort 1, while patients randomised subsequently will be included in Cohort 2. The primary analysis for the four treatment groups maintained in Cohort 2 will combine data from both cohorts, while the accrued data from discontinued treatment groups will be analysed descriptively.

TP-GDO-WW-016-08 CONFIDENTIAL Project Document Version No. 3.0 Effective Date: 26 Nov 19 Project Document Effective Date: Date of last signature Related to: SOP-GDO-WW-019 Page 22 of 50

The change from baseline of the log transformed UACR at the end of 12 weeks of study treatment (Visit 10) will be analysed by a mixed-effects model for repeated measures (MMRM) at Visits 7, 8, 9, and 10. The analysis model will include treatment and visit as fixed effect, the log transformed baseline UACR and the stratifying factors (T2DM [yes/no] and eGFR [ $\geq$  20 to <30 mL/min/1.73 m²; or  $\geq$ 30 to <45 mL/min/1.73 m²; or  $\geq$ 45 mL/min/1.73 m²] as well as the Cohort variable (1 or 2) as covariates. Moreover, treatment  $\times$  visit interaction will also be included in the model.

- 1. The model will involve the following four steps:
  - a) Log-transformation of the UACR:

First, the UACR at baseline and the UACR at post-baseline visits (7, 8, 9, and 10) will be log-transformed. The log-transformed UACR at baseline will then be subtracted from the log-transformed at post-baseline visits to calculate the change of UACR in log units.

b) Execution of the model:

The model will include the change in UACR in log units as a dependent variable and the log-transformed UACR at baseline as covariate, as well as the other independent variables described at the beginning of this section.

- c) Back-transformation of the results from the model:
  - The results from the execution of the model will be back transformed to the original scale after an exponentiation of the means to obtain the percent change from baseline of the treatments. The LS mean difference and its CI between each treatment and dapagliflozin alone will also be back-transformed to yield the percent difference between two treatments with its 95% CI at Visit 10 expressed in percentage.

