### 4.10.1.5 Multiple Comparisons/Multiplicity

The type I error will be controlled at a 2-sided  $\alpha$ =0.05 level for multiplicity. Statistical significance will be assessed in the pre-specified order of the endpoints as specified below. The testing procedure will continue down the hierarchy if the preceding null hypothesis is rejected at a 2-sided  $\alpha$ =0.05 level and will stop if the null hypothesis for the preceding endpoint is not rejected at a two-sided  $\alpha$ =0.05 level.

- 1. Overall comparison of the percentage changes from baseline in UACR at week 12 across all 4 treatment groups (global null hypothesis)
- 2. Each of the 3 doses of AZD9977 in combination with dapagliflozin 10 mg versus dapagliflozin 10 mg in the following order:
  - a. AZD9977 150 mg + dapagliflozin 10 mg versus dapagliflozin 10 mg
  - b. AZD9977 50 mg + dapagliflozin 10 mg versus dapagliflozin 10 mg
  - c. AZD9977 15 mg + dapagliflozin 10 mg versus dapagliflozin 10 mg

TP-GDO-WW-016-08 CONFIDENTIAL Project Document Version No. 3.0 Effective Date: 26 Nov 19 Project Document Effective Date: Date of last signature Related to: SOP-GDO-WW-019 Page 24 of 50

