# 4.13 Determination of Sample Size

A total of 119 evaluable participants per arm will provide 80% power to detect a 30% placebo adjusted change from baseline in UACR at 12 weeks, assuming a standard deviation of 1.0 on the natural log-scale and  $\alpha$ =0.05. To account for approximately 5% drop-out, approximately 500 participants will be randomly assigned to study intervention (125 participants per group) such that approximately 476 evaluable participants (119 per group) complete the study.

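### The stated 80% power covers one pairwise test only; with the overall four-group test that must be rejected first, power to claim 150 mg at the 30% effect is about 61–76%

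*Protocol*

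**What the plan says.** **Sample size.** Protocol 9.2 (repeated in the Synopsis) says "A total of 119 evaluable participants per arm will provide 80% power to detect a 30% difference in a AZD9977 dose group" given with dapagliflozin, relative to dapagliflozin alone, "assuming a SD of 1.0 on the natural log-scale and alpha = 0.05". It randomises 125 per group so that 119 are evaluable after about 5% drop-out. SAP 4.13 repeats 119 per arm and 80%, but words the target as power "to detect a 30% placebo adjusted change from baseline in UACR at 12 weeks".

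**Testing.** Protocol 9.4.2.1 sets a fixed sequence. Its first item is "Overall comparison of the percentage changes from baseline in UACR at week 12 across all 4 treatment groups". The pairwise comparisons with dapagliflozin follow in the order 150, 50 and 15 mg. SAP 4.10.1.5 labels the first item the global null hypothesis and makes the order binding: "The testing procedure will continue down the hierarchy if the preceding null hypothesis is rejected at a 2-sided" 0.05 level; otherwise testing stops.

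**Effect size.** The amendment history (Appendix K, Amendment 5) explains the current sample size by an expected effect that was reduced because the comparator became active. I read that as the 30%. Protocol 4.3 says the three doses are "anticipated to yield an effect on UACR covering the whole dose-response curve from approximately 20 to 60% UACR reduction", without naming the reference. No effect at 15 or 50 mg is tied to the sample size.

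**The concern.** The first dose claim needs two rejections: the overall four-group test and then 150 mg against dapagliflozin. The sample size sections describe only the second. Two tests cannot both reject more often than one of them does, so the chance of claiming 150 mg at the design effect cannot exceed the pairwise power. This is true whatever the dose pattern and whatever form the overall test takes. Only the size of the loss depends on assumptions.

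A reader could take 80% as the chance that the first dose claim succeeds under the planned procedure if the 30% effect is true. Some trials would show a significant 150 mg comparison that cannot be claimed because the overall test missed. The documents do not show how often that happens. This is an omission from the power statement, not a miscalculation.

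**Working it through.** **Inputs from the documents.** 119 evaluable per arm, four equal arms, SD 1.0 on the log scale, 30% difference (ratio 0.70, so δ = |ln 0.70| = 0.3567) and alpha 0.05. That alpha is two-sided comes from SAP 4.10.1.5.

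**Assumptions.** The 30% effect sits at 150 mg. The overall test is a 3-df F test at 0.05, since its form is not named. There is a single time point and no covariates. The 15 and 50 mg effects are varied.

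**Step 1: the plan's own figure.**
- Standard error = 1.0 × √(2/119) = 0.1296.
- δ/SE = 0.3567/0.1296 = 2.751.
- Normal approximation: Φ(2.751 − 1.960) = Φ(0.791) = 78.6%.
- Noncentral t: 78.2% with two arms; 78.4% with the variance pooled over four arms (472 df).

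The stated 80% is reproduced to within 2 points. Exactly 80% needs 2 × (1.960 + 0.842)² / 0.3567² = 123.4, so 124 per arm (125 by t), or a difference of 30.5–30.6%, or an SD of 0.978–0.982. That gap is at rounding level.

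**Step 2: overall test.** Write the effects at 0/15/50/150 mg as shares pᵢ of δ. The noncentrality is λ = 119 × 0.3567² × S = 15.14 × S, where S = Σ(pᵢ − p̄)².

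**Step 3: both tests.** 1,000,000 simulated trials per pattern: the F test, then 150 mg against dapagliflozin with pooled variance, two-sided 0.05. The overall-test power agreed with the exact noncentral F.

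| Assumed pattern (15, 50, 150 mg as shares of δ) | S | λ | Overall test alone | Both tests, 119/arm, SD 1.0 | Both, SD 0.98 | Both, 125/arm, SD 1.0 | Effect at 150 mg for 80% through both (119/arm, SD 1.0) |
|---|---|---|---|---|---|---|---|
| Only 150 mg works (0, 0, 1) | 0.75 | 11.4 | 81.4% | 72.2% | 74.3% | 74.7% | 32.1% |
| All doses equal (1, 1, 1) | 0.75 | 11.4 | 81.4% | 72.2% | 74.2% | 74.7% | 32.0% |
| 50 = 150 mg, 15 mg null (0, 1, 1) | 1.00 | 15.1 | 91.7% | 76.4% | 78.3% | 78.6% | 31.0% |
| Equal log steps (1/3, 2/3, 1) | 0.56 | 8.4 | 67.4% | 64.3% | 66.5% | 66.9% | 34.1% |
| 15 and 50 mg at half (0.5, 0.5, 1) | 0.50 | 7.6 | 62.3% | 60.9% | 62.9% | 63.4% | 35.1% |

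If the lower doses lie between no effect and the 150 mg effect, S is smallest when both sit at half and largest when one is null and the other full. The table therefore contains both extremes of the overall test. Seven further patterns of this kind fell within the same 61–76% range, to simulation error.

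**Step 4: cost of the overall test itself.** Measured from the 78.4% pairwise power: 78.4 − 76.4 = 2.0 points at best, 78.4 − 60.9 = 17.5 points at worst, and 78.4 − 64.3 = 14.1 points with equal log steps.

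**Step 5: larger effects.** At 119 per arm and SD 1.0, true reductions of 20/30/40% against dapagliflozin give 93.7% through both tests, and 20/40/60% gives 100.0% to one decimal.

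**The case against.** **The sentence is already pairwise.** Protocol 9.2 refers to a single dose group against dapagliflozin alone, and power per comparison is conventional. No sentence calls 80% the success probability of the sequence. That is fair, and it is why this is an omission. But the plan puts a specified test ahead of every dose claim, and the sample size sections do not mention it.

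**The range rests on assumptions outside the documents.** No section places the 30% at 150 mg or gives effects at the lower doses. The 61% is the floor: it needs 15 and 50 mg to act identically and 150 mg to double their log effect. Read against dapagliflozin, the 20 to 60% in Protocol 4.3 implies ample power. All of this stands as a limit on the size. It does not change the direction, and the stated power is for 30%, so that is where it should be judged. A graded response in equal log steps is no contrivance in a dose-response study, and it gives about 64%.

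**Part of the gap to 80% is not due to the overall test.** This is correct: 1.5 to 2 points come from 119 being slightly short for the pairwise test. At SD 0.98, which restores 80% pairwise, power through both tests is still 63–78%.

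**The planned mixed model may do better.** It adjusts for baseline and uses Visits 7 to 10, and some drop-outs contribute data. With all 125 per arm evaluable, an upper bound, pairwise power is 80.4% and power through both tests is 63–79%. At an illustrative SD of 0.9, power through both tests is 72–85%, but pairwise power rises too: 0.3567/(0.9 × 0.1296) = 3.06, giving Φ(1.10), or about 86%. The gap remains. The documents do not say whether SD 1.0 is already covariate-adjusted.

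**Conclusion.** The concern holds. The 80% describes one comparison with dapagliflozin, not the procedure by which 150 mg can be claimed. At the design effect, power through both tests is about 61–76%, against 78.2–78.6% pairwise. These sizes rest on the 30% effect being at 150 mg, an overall 3-df F test, SD 1.0, 119 evaluable per arm, and lower-dose effects between none and the 150 mg effect. That power falls short of the pairwise figure by some amount does not rest on them. Type I error is not affected. If true effects against dapagliflozin approach the upper part of the range in Protocol 4.3, the trial is well powered even so.

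A separate editorial error is confirmed. SAP 4.13 describes a placebo-adjusted target, but the placebo arm has been dropped and Protocol 9.2 and SAP 4.10.1.5 compare with dapagliflozin alone, as does SAP 4.10.1.1: "The LS mean difference and its CI between each treatment and dapagliflozin alone will also be back-transformed".

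**What to change.** Keep 500 randomised and leave the analysis unchanged. In the Synopsis, Protocol 9.2 and SAP 4.13:

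1. State that the power is for one pairwise comparison with dapagliflozin 10 mg alone, at two-sided alpha 0.05, before the overall test is taken into account.
2. Give it as about 78% for a 30% difference, or as 80% for a difference of about 30.6%. Keep 80% for 30% only if a covariate-adjusted SD of about 0.98 can be supported by data; it should not be back-solved.
3. Add the power to claim 150 mg through the overall test under a named dose pattern, and name the form of that test.
4. In SAP 4.13, replace the placebo wording with the comparison with dapagliflozin 10 mg alone.

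The cost is a few sentences and one short simulation. The only drawback is a less favourable stated power.

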4 STUDY DESIGN

4.1 Overall Design

This is a Phase 2b, multi-centre, randomised, double-blind, active-controlled parallel group, study to assess the efficacy, safety and tolerability of AZD9977 and dapagliflozin administered for 12 weeks in patients with HF and CKD (eGFR ≥ 20 and $\le 60 \text{ mL/min/1.73 m}^2$, with at least 20 % of patients with eGFR $\ge 20 \text{ to } < 30 \text{ mL/min/1.73 m}^2$ and a maximum of 35% of patients with eGFR $\ge 45 \text{ mL/min/1.73 m}^2$).

The study will be conducted at approximately 150 to 250 sites in approximately 20 countries including North America, Asia/Pacific, and European countries.

For each participant, the total duration of participation will be approximately 22 to 24 weeks, including a 1-week screening period, followed by up to 7-week run-in period followed by a 12-week treatment period (including 6 visits), the EOT visit, and a 4-week safety follow-up after last dose (including 1 visit). An optional pre-screening visit may be scheduled. Week and day for pre-screening visit will be at the discretion of the investigator.

After screening, eligible participants currently on treatment with a SGLT2i other than dapagliflozin should stop taking the SGLT2i and start on dapagliflozin 10 mg. Participants on dapagliflozin treatment will continue on treatment but the medication will be provided. Participants will then undergo a 4 to 5-week run-in period to ensure washout of forbidden medications and stable doses of allowed background medications.

For participants eligible after screening not on treatment with a SGLT2i, treatment with dapagliflozin 10 mg will be initiated. Participants will then undergo a 6 to 7-week run-in period to ensure washout of forbidden medications and stable doses of allowed background medications.

During the treatment period, participants will be randomly assigned in a 1:1:1:1 ratio to receive once daily administration of one of the 4 study treatments as described below. To ensure blinding, the study treatment will be administered in the form of 3 oral capsules and 1 oral tablet in the following combinations.

Study Treatment	Capsule 1	Capsule 2	Capsule 3	Tablet
AZD9977 15 mg + Dapagliflozin 10 mg	AZD9977 15 mg	Placebo	Placebo	Dapagliflozin 10 mg
AZD9977 50 mg + Dapagliflozin 10 mg	Placebo	AZD9977 50 mg	Placebo	Dapagliflozin 10 mg
AZD9977 150 mg + Dapagliflozin 10 mg	Placebo	AZD9977 50 mg	AZD9977 100 mg	Dapagliflozin 10 mg

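### On the plan's own inputs, 119 evaluable per arm give about 78% power rather than the stated 80%, and SAP 4.13 describes the effect as placebo-adjusted although the comparator is dapagliflozin alone

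*Protocol*

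**What the plan says.** Protocol 9.2, repeated in the Statistical Methods part of the synopsis (1.1), says: "A total of 119 evaluable participants per arm will provide 80% power to detect a 30% difference", the difference being for one AZD9977 dose group plus dapagliflozin "compared to dapagliflozin 10 mg alone in percent change from baseline in UACR at 12 weeks". The remaining inputs follow: "assuming a SD of 1.0 on the natural log-scale and alpha = 0.05". To allow for about 5% drop-out, 125 per group (500 in total) are randomised so that 119 per group (476) are evaluable.

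SAP 4.13 has the same 119, SD, alpha, drop-out rate and total of 500, but words the effect differently: "80% power to detect a 30% placebo adjusted change from baseline in UACR at 12 weeks".

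Three other places fix how the calculation must be read. Protocol 9.4.2.1 sets the scale: "As UACR is assumed to follow a log-normal distribution, it will be log transformed for statistical analysis purposes". SAP 4.10.1.5 sets the sidedness, "The type I error will be controlled at a 2-sided" level of 0.05, and makes the tests a fixed sequence: "The testing procedure will continue down the hierarchy if the preceding null hypothesis is rejected". Protocol 4.1 sets equal allocation: "participants will be randomly assigned in a 1:1:1:1 ratio".

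**The concern.** A sample-size statement should follow from the inputs printed beside it. Here the usual two-group calculation asks for 124 or 125 evaluable per arm, not 119. The documents therefore claim slightly more power at the evaluable number than their inputs deliver. The t-test requirement of 125 is also the number randomised, which raises the question of whether the 80% was worked out for the randomised number and then attached to the number left after drop-out.

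The SAP wording is a separate fault. Protocol 9.2 and the SAP's own primary comparisons (4.10.1.1 and 4.10.1.5) are against dapagliflozin 10 mg. Placebo alone is not one of the four current arms, and data from the discontinued arms are only to be described. The protocol's amendment history (Appendix K, Amendment 5) records that the expected effect was reduced because the comparator became an active drug, so SAP 4.13 attaches the 30% to a comparison that is no longer a primary one.

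At stake is the accuracy of a stated design property and the agreement of the two documents on what the trial is powered for. No estimate, test or error rate is affected.

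**Working it through.** **Inputs**

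- Effect: 30% lower UACR than with dapagliflozin alone (Protocol 9.2). The analysis is on the log scale and is back-transformed to a percent difference (Protocol 9.4.2.1, SAP 4.10.1.1), so I read this as a ratio of 0.70. Then delta = −ln(0.70) = 0.3567.
- SD 1.0 on the natural log scale, alpha 0.05 (Protocol 9.2).
- Two-sided (SAP 4.10.1.5). In the fixed sequence each pairwise test uses the full 0.05.
- Equal allocation, 119 evaluable per arm.

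The calculation is for one pairwise comparison. It does not include the global test that comes first in the sequence.

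**Attempt to reproduce 80% at 119 per arm**

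- Normal approximation: delta / (SD × √(2/n)) = 0.3567 / √(2/119) = 2.751. Then 2.751 − 1.960 = 0.791, and Φ(0.791) = **78.6%**.
- Two-group t-test (noncentral t, 236 df): **78.2%**. With the error df pooled over four arms (472 df): 78.4%.

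**Number per arm for 80%**

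- Normal: n = 2 × (1.960 + 0.8416)² / 0.3567² = 123.4, so **124**.
- t-test: 124 gives 79.9% and 125 gives 80.2%, so **125**.

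**Difference detectable with 80% power at 119 per arm**

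- Normal: delta = (1.960 + 0.8416) × √(2/119) = 0.3632, and 1 − exp(−0.3632) = 30.5%.
- t-test: delta = 0.3647, and 1 − exp(−0.3647) = 30.6%.

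**SD at which 119 per arm would give 80%**

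- Normal: 0.3567 / 0.3632 = 0.982.
- t-test: 0.3567 / 0.3647 = 0.978.

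**Other readings of the inputs**

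| Reading | n per arm for 80% (normal) | Power at 119 (normal) |
|---|---|---|
| One-sided 0.05 | 98 | 86.6% |
| delta = 0.30 on the log scale | 175 | 63.8% |
| delta = ln 1.3 | 229 | 52.5% |

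None of these returns 119.

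**Drop-out step**

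- From 125 down: 125 × 0.95 = 118.75, about 119.
- From 119 up: 119 × 1.05 = 124.95, about 125. Dividing instead, 119 / 0.95 = 125.3.
- 476 / 500 = 95.2%.

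The pair 119 and 125 therefore agrees with about 5% drop-out in either direction. The figures cannot show which of the two was the starting point.

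**The case against.** The strongest defence is that the gap is trivial for a planning figure. It is under 2 points and rests on an assumed SD. An SD of about 0.98, or a difference of 30.5% to 30.6%, closes it.

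Nor is the two-group formula the planned analysis. The primary model is an MMRM over Visits 7 to 10, adjusted for log baseline UACR, T2DM, eGFR stratum and cohort. The documents do not say whether the SD of 1.0 is before or after adjustment. If it is before, covariates explaining about 4% of the variance would be enough (1 − 0.978² = 0.043, by t-test). The documents give no correlation, so this remains a possibility. All of this stands, and it sets the severity. It does not make the printed sentence follow from its printed inputs.

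On the SAP wording, the defence is that this is a single phrase, that every analysis section names dapagliflozin as comparator, and that the control arm does take placebo capsules with its dapagliflozin. It is indeed editorial. But SAP version 3.0 was revised for protocol versions 6.0 and 7.0, and SAP 4.14 declares no change to the planned analysis, so the phrase looks like a leftover and should be aligned.

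A reader might go further and infer that the 5% drop-out was subtracted from the requirement instead of being added to it. The match between 125 randomised and the t-test requirement of 125 is consistent with that, but neither document shows a derivation, and Protocol 9.2 presents 119 as the requirement and 125 as the allowance for drop-out. A reader might also infer that the stated power holds only if nobody drops out. That does not follow either: the efficacy set is all randomised participants (Protocol 9.3), and the MMRM uses every available UACR value under a missing-at-random assumption (SAP 4.10.1.1), so someone who leaves after Visit 7, 8 or 9 still contributes.

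**Conclusion.** The point holds as a minor correction. With a ratio of 0.70, log-scale SD 1.0, two-sided alpha 0.05 and a simple two-group comparison, 119 evaluable per arm give 78.2% (t-test) to 78.6% (normal) power, which is 1.4 to 1.8 points below the stated 80%. The stated power corresponds to 125 or 124 evaluable per arm, or to a difference of about 30.6% with 119.

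This rests on reading the 30% as a ratio on the log scale, and on the SAP's two-sided level applying to the sample-size statement, which does not itself give the sidedness. It does not show that the trial is materially underpowered: the planned model may recover the difference, and the calculation leaves out both that gain and the global test at the head of the sequence.

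The placebo-adjusted wording in SAP 4.13 is wrong for the current design, whatever the power figure.

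**What to change.** - In Protocol 1.1, Protocol 9.2 and SAP 4.13, state that 119 evaluable per arm give about 78% power at a two-sided 5% level for a 30% lower UACR than with dapagliflozin 10 mg alone. Add that 80% power corresponds to 125 evaluable per arm, or to a difference of about 30.6% with 119.
- In SAP 4.13, replace the placebo-adjusted change with a 30% difference versus dapagliflozin 10 mg alone.

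If the sponsor has a derivation that gives 80% at 119, for example one that counts covariate adjustment, stating it and saying whether the SD of 1.0 is adjusted would serve equally well.

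The cost is wording in two documents and a slightly less favourable power figure. Enrolment, the analysis model and the test sequence do not change.
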